2.5.4 Supportive analyses

Sensitivity analyses will be performed as follows:

(A) Co-primary endpoints (PASI 75 and IGA 0 or 1 response at Week 12) and key secondary endpoints will be evaluated using the logistic regression as described in primary analysis method with non-responder imputations instead of multiple imputation for missing values.

2.6 Analysis of the key secondary objective

2.6.1 Key secondary endpoint

The key secondary endpoint of this study is PASI 90 response at Week 12.

2.6.2 Statistical hypothesis, model, and method of analysis

Testing strategy

As stated in [Section 2.5.2](#), the hypotheses H_1 and H_2 will be included in co-primary testing procedure. Each hypotheses is tested at $\alpha = 2.5\%$ (one-sided). The testing sequence will continue to key secondary endpoint PASI 90 at $\alpha = 2.5\%$ (one-sided) only if both H_1 and H_2 have been rejected at α (one-sided) such that a family-wise type-I-error of α (one-sided) is kept.

H_3 : secukinumab 300 mg (2 mL AI) is not superior to placebo with respect to PASI 90 response at Week 12

PASI 90 response will be analyzed analogously to the primary endpoints at Week 12, i.e., the logistic regression model with treatment group, baseline bodyweight strata and baseline PASI score as exploratory variables. Odds ratios will be computed for comparisons of secukinumab versus placebo utilizing the logistic regression model fitted.

2.6.3 Handling of missing values/censoring/discontinuations

See [Section 2.5.3](#).

2.7 Analysis of secondary efficacy objective(s)

2.7.1 Secondary endpoints

PASI 50, PASI 75, PASI 90, PASI 100, and IGA mod 2011 0 or 1 response over time

Summary statistics for PASI 50, PASI 75, PASI 90, PASI 100, and IGA mod 2011 0 or 1 response by visit will be presented in contingency tables and will include absolute and relative frequencies. Confidence intervals for response rates will be derived as well based on the exact method.

For PASI 50, PASI 75, PASI 90, PASI 100, and IGA mod 2011 0 or 1 response at each visit, up to Week 12, comparisons between 2mL AI vs placebo and 2mL AI vs 1mL PFS x 2 will be conducted using logistic regression model with treatment group, body weight stratum and baseline PASI as effects.

For PASI 50, PASI 75, PASI 90, PASI 100, and IGA mod 2011 0 or 1 response, the placebo adjusted response rates (i.e., risk difference) including 95% confidence interval (based on normal approximation) will be derived by visit, up to Week 12. In addition, Fisher's exact test will be applied to the treatment group comparisons between 2mL AI versus placebo. In addition, the risk difference between 2ml AI group vs. 1ml PFS group, including 95% confidence interval (based on normal approximation) may be derived by visit, up to Week 52.

Figures will be provided as well displaying estimates for response rates over time by treatment including 95% confidence intervals.

PASI score over time

Summary statistics will be provided for absolute PASI scores as well as for percent change from baseline by visit and treatment group. Figure will be provided for percentage changes in PASI scores over time.

IGA mod 2011 score over time

Summary statistics for the IGA mod 2011 score over time will be presented by visit and by treatment group in contingency tables. Figures will also be provided.

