5.4.3 Logistic regression

Binary outcome variables, including PASI 50 / 75 / 90 / 100 response and IGA mod 2011 0 or 1 response, will be evaluated using a logistic regression model with treatment regimen, baseline bodyweight strata and baseline PASI score. Odds ratios will be computed for comparisons of secukinumab dose regimen versus placebo utilizing the logistic regression model fitted.

If response rates are 0% or 100% in one of the treatment groups, Fisher's exact test will be applied. Confidence intervals for risk difference will be derived based on the exact method. Odds ratio estimate and p-values will not be displayed in outputs, but “-” will be shown.

The odds ratio will be calculated such that an odds ratio >1 is favorable for secukinumab. Using PROC GENMOD to calculate the confidence interval for the odds ratios assumes asymptotic normality of the Wald estimate for the regression coefficient. The 95% confidence interval for the regression parameter of the active treatment effect relative to control(s) will be calculated using an exponential transformation to create the confidence interval for the odds ratio.

All p-values reported on linear hypotheses about regression coefficients will be based on the Wald tests from Type III analyses. In the SAS procedure PROC GENMOD, a Type III analysis will be performed by adding the model options: TYPE3, DIST=BIN, and LINK=LOGIT.

Logistic regression will be applied to response variables at each visit.

If logistic regression model does not converge, the following steps will be performed:

4. Run the PROC GENMOD procedure with EXACT statement;
5. If convergence not reached, remove the covariates from the model one by one until convergence is reached; start with continuous covariates (i.e., baseline bodyweight by replacing with body weight stratum, and then baseline PASI score, followed by removing categorical covariates(i.e., weight stratum);
6. If convergence not reached, perform Fisher's exact test.

It should be noted that this model might not converge if response rates are too low.

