5.4.5.4 Risk difference and $100*(1-\alpha)\%$ confidence interval

For an investigational drug group with n_1 subjects at risk, independent from the control group (e.g., placebo or comparator) with n_0 subjects at risk, of whom x_1 and x_0 experience a certain event, the risk difference is estimated as $p_1 - p_0$ with $p_1 = x_1/n_1$ and $p_0 = x_0/n_0$.

Exact unconditional confidence limits for the risk difference will be obtained with SAS procedure PROC FREQ and option RISKDIFF in the TABLES statement, specifying the RISKDIFF option also in the EXACT statement.

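### The SAP's by-visit risk-difference intervals use a normal approximation with no sparse-data rule, which conflicts with its own 0%/100% rules and is inaccurate when response rates are very low and unequal

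*SAP*

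**What the plan says.** SAP 2.7.1 sets the interval for the by-visit difference between the 2 mL auto-injector (AI) and placebo: "based on normal approximation) will be derived by visit, up to Week 12". For AI against the pre-filled syringe (PFS) the same method is optional: "based on normal approximation) may be derived by visit, up to Week 52". A test is to stand beside the placebo comparison: "In addition, Fisher's exact test will be applied to the treatment group comparisons between 2mL AI versus placebo". The exact method named in the same section is for single-arm rates: "Confidence intervals for response rates will be derived as well based on the exact method".

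Other sections bear on the same tables:

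- **SAP 5.4.3** covers these response variables ("Logistic regression will be applied to response variables at each visit") and has a boundary rule: "If response rates are 0% or 100% in one of the treatment groups, Fisher's exact test will be applied". The next sentence is "Confidence intervals for risk difference will be derived based on the exact method".
- **SAP 2.5.2** has a different boundary rule for the co-primary analysis: a t-test-based interval under multiple imputation, and Fisher's test under non-responder imputation.
- **SAP 5.4.2** asks for the by-visit risk difference with a 95% interval and names no method.
- **SAP 5.4.4** makes multiple imputation the by-visit method. Its sample code pools the asymptotic standard error of the risk difference when the logistic model does not converge.

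SAP 2.1 says confidence intervals serve estimation and not decisions.

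**The concern.** The Wald interval estimates its own variance from the observed proportions. When those are at or near 0%, the estimated variance is zero or too small. Efficacy is analysed from Week 1 (window Day 2 to 11, SAP Table 2-3), and the endpoints include PASI 90 and PASI 100, so sparse tables are plausible in the first weeks. SAP 2.7.1 prescribes the Wald interval there without exception.

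Two things are at stake. A table could show an interval of zero width for 0/40 against 0/40, or intervals far below their nominal coverage. And for a visit with an empty arm, three sections point to three intervals, so a programmer cannot tell which one to produce.

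**Working it through.** **Inputs from the documents.** Allocation is 2:2:1:1 in about 120 subjects, with the two placebo groups pooled up to Week 12 (Protocol 6.1.3). That gives 120 × 2/6 = 40 AI and 20 + 20 = 40 placebo, the 40 per group of SAP 3.1. The Week 12 planning rates are 62% vs 8% (PASI 75), 55% vs 8% (IGA 0/1) and 46% vs 8% (PASI 90).

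**Plan's own figure.** Enumerating two Binomial(40, p) arms with one-sided Fisher's exact test at 2.5% gives power of 99.97% (62% vs 8%), 99.7% (55% vs 8%) and 97.3% (46% vs 8%). The stated powers (above 99%, above 99%, above 90%) reproduce, so the set-up is right.

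**Interval under SAP 2.7.1.** With d = p1 − p0:

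d ± 1.96 × √[p1(1 − p1)/40 + p0(1 − p0)/40]

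*Both arms empty, 0/40 vs 0/40.* d = 0 and both variance terms are 0, so the interval is (0, 0). The Newcombe hybrid score interval is −8.8 to +8.8 points.

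*One arm empty, 4/40 vs 0/40.* d = 0.10; SE = √(0.10 × 0.90/40) = 0.0474; interval 0.10 ± 0.093, that is 0.7 to 19.3 points. The two-sided Fisher p-value beside it is 0.116. Newcombe: −0.6 to 23.1.

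*No empty arm, 6/40 vs 1/40.* d = 0.15 − 0.025 = 0.125; SE = √(0.1275/40 + 0.0244/40) = 0.0616; interval 0.125 ± 0.121, that is 0.4 to 24.6 points. Fisher p = 0.108. Newcombe: −0.6 to 26.7.

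**Coverage.** For true rates (p1, p0), coverage is the sum, over all 41 × 41 tables whose interval contains p1 − p0, of the product of the two binomial probabilities. The chance of zero width from two empty arms is (1 − p1)^40 × (1 − p0)^40. For 2% vs 0.5% that is 0.446 × 0.818 = 0.365. All rates except the three Week 12 rows are assumptions.

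| True rates, AI vs placebo | Wald coverage | Zero width | Newcombe coverage |
|---|---|---|---|
| 2% vs 0.5% | 63.4% | 36.5% | 99.99% |
| 3% vs 1% | 78.0% | 19.8% | 99.9% |
| 5% vs 1% | 86.9% | 8.6% | 99.7% |
| 10% vs 1% | 90.8% | 1.0% | 97.0% |
| 20% vs 1% | 94.0% | about 0 | 96.9% |
| 1% vs 1% | 99.9% | 44.8% | 99.99% |
| 62% vs 8% (Week 12) | 93.8% | about 0 | 94.8% |
| 55% vs 8% (Week 12) | 94.7% | about 0 | 95.0% |
| 46% vs 8% (Week 12) | 94.0% | about 0 | 95.2% |

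**Where the misses fall.** Splitting the Wald misses by whether an arm is at 0% or 100%:

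| True rates | Misses at a boundary (points) | Other misses (points) |
|---|---|---|
| 2% vs 0.5% | 36.62 | 0.00 |
| 3% vs 1% | 22.02 | 0.01 |
| 5% vs 1% | 13.08 | 0.04 |
| 10% vs 1% | 6.91 | 2.32 |

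**The case against.** The strongest reply is that SAP 5.4.3 already covers the bad cases. It names these endpoints, applies at each visit, and calls for exact limits once an arm is at 0% or 100%. The split above shows that nearly all misses at the lowest rates are of that kind, so if 5.4.3 governed, most of the coverage loss would disappear. This is correct as arithmetic, but it does not settle the matter. SAP 2.7.1 is the section specific to these intervals; it states the normal approximation without exception and does not refer to 5.4.3. SAP 2.5.2 gives a t-test-based interval for the same boundary case under multiple imputation, and the code in 5.4.4 pools an asymptotic standard error. Which rule prevails is not stated.

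Disagreement with Fisher's test is weaker evidence than it looks, because Fisher's test is conservative. One exact unconditional interval (score-based) for 4/40 vs 0/40 is 0.5 to 23.7 points and also excludes zero. Newcombe reduces such disagreements without removing them: at 5/40 vs 0/40 it gives 1.3 to 26.1 with Fisher p = 0.055.

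A reader might also infer more than the documents support:

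- **That early response rates are near zero.** Neither document gives a rate before Week 12. It is plausible for PASI 90/100 and IGA 0/1 in the first weeks, less so for PASI 50.
- **That coverage is poor at all low rates.** Equal tiny rates over-cover (1% vs 1%: 99.9%).
- **That one empty arm collapses the interval.** Zero width needs both arms at a boundary.
- **That the protocol and SAP promise exact limits throughout.** Protocol 12.4.2 concerns the co-primary analysis. SAP 5.4.5.4 ("Exact unconditional confidence limits for the risk difference will be obtained") sits under crude incidence.
- **That plotted error bars would be wrong.** The planned response figures show rates by treatment, not these differences.

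**Conclusion.** The point holds as a matter of reporting accuracy and internal consistency. SAP 2.7.1 gives no sparse-data rule for the by-visit risk differences, and it conflicts with 5.4.3, and with the 2.5.2 rule where that is carried over to by-visit tables, whenever an arm is at 0% or 100%. With 40 per arm the prescribed interval is (0, 0) when neither arm has a responder. Coverage is about 63% to 91% over assumed true rates from 2% vs 0.5% to 10% vs 1%. The size of the problem rests on those assumed early-visit rates and on 2.7.1 being applied as written.

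At the Week 12 planning rates the shortfall is small (93.8% to 94.7% against 95%). H1 to H3 are tested by other means and are unaffected. No decision rests on these intervals, but SAP 2.1 gives estimation as their purpose, and that is what fails when data are sparse.

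**What to change.** 1. In SAP 2.7.1, replace the normal approximation with the Newcombe hybrid score interval for all by-visit risk differences, including AI against PFS if it is produced.
2. Give the form for multiply imputed data. Exact limits do not pool directly by Rubin's rules, and putting pooled proportions straight into the score formula omits between-imputation variance. One workable form takes Wilson limits per arm, with the sampling variance inflated by Rubin's relative increase in variance (set to zero when every imputation gives 0% or 100%), and combines the arms by Newcombe's formula. For non-responder-imputed data, Newcombe or exact limits can be used directly. If exact limits are chosen, name the variant: for 0/40 vs 0/40 the score-based version gives ±9.0 points and the unstandardized version ±22.8.
3. State one 0%/100% rule and align SAP 2.5.2, 2.7.1, 5.4.2, 5.4.3 and the code in 5.4.4 with it.

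The cost is SAP wording, a minor code change and somewhat wider intervals at low rates. Newcombe is itself conservative there (97% to nearly 100% in the low-rate rows above).

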2.7.2 Statistical hypothesis, model, and method of analysis

Not applicable.

2.7.3 Handling of missing values/censoring/discontinuations

See [Section 2.5.3](#).

2.8 Safety analyses

All safety analyses will be based on the safety set. Only those scheduled visits which were pre-planned in the protocol will be reported in tables and figures for safety variables.

Treatment groups for evaluation of entire treatment

The summaries of evaluation will be reported for treatment period 1 and entire treatment period, respectively. Week 16 primary analysis will include data up to Week 12 for treatment period 1 and data up to Week 16 last patient last visit (LPLV) for the entire treatment period.

The following groups will be used for treatment period 1:

- **AIN457 300 mg (2mL AI)**: all subjects who are randomized to 300 mg 2mL AI group at Randomization visit
- **AIN457 300 mg (2x1mL PFS)**: all subjects who are randomized to 300 mg 2x1mL PFS group at Randomization visit
- **Placebo**: all subjects who are randomized to a placebo group at Randomization visit
- **Any AIN457 300 mg**: Any AIN457 300 mg of (2mL AI) or (2x1mL PFS) as above.

The following groups will be used for entire treatment period:

- **AIN457 300 mg (2mL AI)**: all subjects who are randomized to 300 mg 2mL AI group at Randomization visit
- **AIN457 300 mg (2x1mL PFS)**: all subjects who are randomized to 300 mg 2x1mL PFS group at Randomization visit
- **Any AIN457 300 mg (2mL AI)**: all subjects who are randomized to 300 mg 2mL AI group at Randomization visit and all placebo subjects who are re-assigned to 300 mg 2mL AI at Week 12, but they are only considered after the treatment re-assignment (Week 12 treatment injection).
- **Any AIN457 300 mg (2x1mL PFS)**: all subjects who are randomized to 300 mg 2x1mL PFS group at Randomization visit and all placebo subjects who are re-assigned to 300 mg 2x1mL PFS at Week 12, but they are only considered after the treatment re-assignment (Week 12 treatment injection).
- **Any AIN457 300 mg**: Any AIN457 300 mg of (2mL AI) or (2x1mL PFS) as above.
- **Placebo**: all subjects who are re-assigned will only be considered until the re-assignment point (Week 12 treatment injection).

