Other Secondary Objective(s) 
To assess the efficacy of secukinumab 300 mg when administered in 2 mL AI in subjects with plaque-type psoriasis with respect to PASI score, IGA mod 2011 score, PASI 50 / 75 / 90 / 100 and IGA mod 2011 0 or 1 response up to Week 12 compared to placebo, and over time up to Week 52.To investigate the clinical safety and tolerability of secukinumab 300 mg 2 mL AI as assessed by vital signs, clinical laboratory variables, and adverse events monitoring, compared to placebo.To assess the subject usability (ability to follow instructions for use and potential use-related hazards) and satisfaction with the new secukinumab 2 mL AI utilizing a self-administered SIAQ and investigator/site staff observation of secukinumab 300 mg 2 mL AI administration.To investigate the effects of secukinumab 300 mg when administered in 2 mL AI with respect to DLQI 0 or 1 achievement and DLQI changes at Week 12 compared to placebo, and over time up to Week 52.	Endpoint(s) for other secondary objective(s) 
PASI score and IGA mod 2011 score at each visit up to week 52PASI 50, PASI 75, PASI 90, PASI 100 and IGA mod 2011 0 or 1 response at each visit up to week 52Treatment emergent adverse events, change from baseline to each study visit in clinical laboratory variables and vital signsSuccessful self-injection, subject use errors, item and domain scores from the SIAQ, change in SIAQ domain scoresDLQI 0 or 1 score at each visitChange from baseline in each of the seven DLQI scores and in the DLQI total score

Objective(s)	Endpoint(s)

3 Study design

This is a multicenter, randomized, double-blind, placebo-controlled, parallel-group trial in approximately 120 subjects with moderate to severe plaque-type psoriasis.

It is expected that subjects will be enrolled at around 30 study sites worldwide.

The study consists of 3 periods:

- Screening Period (of at least 1 week and up to 4 weeks between Screening and Randomization)

The screening period is used to assess eligibility of the subjects and to taper subjects off prohibited medications.

- Treatment Period 1 (of 12 weeks, double-blind between Randomization and Week 12 pre-dose)

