12.6.2 Safety Endpoints

All safety evaluations will be performed on the safety set.

Analysis of adverse events will be based on treatment emergent events, which are defined as events started after the first dose of study treatment and within 84 days after the last study treatment, or events present prior to the first dose of study treatment but increased in severity based on preferred term within 84 days after the last study treatment.

Other safety variables will be based on on-treatment events, which are defined as any events that happened after first dose of study treatment and on or before last dose + 84 days.

Adverse events

Treatment emergent AEs will be summarized for each treatment group by presenting the number and percentage of subjects with all/any AEs, AEs in each primary system organ class and each individual AE (preferred term). Summaries will also be presented for AEs by severity and for study treatment related AEs. If a subject reported more than one adverse event with the same preferred term, the adverse event with the highest severity will be presented. If a subject reported more than one adverse event within the same primary system organ class, the subject

will be counted only once with the highest severity at the system organ class level, where applicable.

Tabulated summaries will be presented for Treatment Period 1 and for the entire study (Treatment Period 1 combined with Treatment Period 2)

Confidence intervals for relative frequencies will be derived as well according to the score method including continuity correction by [Newcombe 1998](#).

Separate summaries will be provided for death, serious adverse event, other significant adverse events leading to discontinuation and adverse events leading to study treatment discontinuation.

A graphical display of relative frequencies within system organ classes will be presented.

Exposure adjusted analyses in terms of incidence rate will be provided combining all the study periods.

Laboratory data

The summary of laboratory evaluations will be presented for three groups of laboratory tests (hematology and serum chemistry). Descriptive summary statistics for the change from baseline to each study visit will be presented. These descriptive summaries will be presented by test group, laboratory test and treatment group. Change from baseline will only be summarized for subjects with both baseline and post baseline.

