- Group 4: Placebo - Secukinumab 300 mg (2 x 1 mL PFS): placebo treatment administered as two 1 mL placebo secukinumab plus one 2 mL AI matching placebo secukinumab s.c. injections once weekly at Randomization, Weeks 1, 2, and 3, followed by dosing every four weeks till week 8. Prior to receiving the Week 12 dose, PASI 90 response will be evaluated. PASI 90 responders will receive placebo every four weeks from week 12 till week 48, except

for weeks 13, 14, and 15 subjects will self-administer a weekly dose of two 1 mL placebo secukinumab 150 mg PFS plus one 2 mL AI matching placebo secukinumab s.c. injections. The PASI 90 non-responders will be assigned to Secukinumab 300 mg (2 mL PFS) group and receive their treatment every four weeks from week 12 till week 48, except for weeks 13, 14, and 15 where the patients will self-administer a weekly dose of the Secukinumab 300 mg (2 mL PFS) group treatment.

[figure not shown]
The following study periods will be considered for analysis:

- **Screening period** (before Randomization)
- **Treatment period 1** (Randomization to Week 12 pre-dose)
- **Treatment period 2** (Week 12 dose to Week 52)
- **Entire treatment period** (Randomization to Week 52, last dose at Week 48)

Of note, no follow-up period is included in this study.

The primary analysis will be provided at the time of Week 16 interim DBL. Treatment period up to Week 16 will be presented for the W16 primary analysis and all data will be presented for the final analysis. The study design is presented in [Figure 3-1](#).

Figure 3-1 Study design

In the figure, the solid arrow means active drug dosing while the dotted arrow means placebo dosing.

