2.8.1 Adverse events (AEs)

For adverse events and other binary safety variables crude incidence and exposure time-adjusted incidence will be derived as described below and summarized in [Table 2-8](#).

All adverse events are summarized based on treatment emergent only. The definition for “treatment emergent” is as below:

- events started after the first dose of study medication or events present prior to the first dose of study medication but increased in severity based on preferred term
- and started prior to the last dose plus 84 days (inclusive)

All adverse events will be listed with “treatment emergent” flag displayed.

Table 2-8 Overview of analyses on some safety endpoints

Analysis period	AEs & SPP/RMP risks	SAEs	AEs-SMQ	AEs by severity	study treatment related AEs, death & other significant AEs	notables (lab/vitals)
treatment period 1 (up to week 12)	•crude incidence	•crude incidence				
Entire treatment period (including all data)	•crude incidence •exp.time adjusted incidence*	•crude incidence	•crude incidence			

*Note, Exposure adjusted incidence rates will be provided and follow the guideline as below:

- Primary SOC level for AE and SAE
- Level 1 for risks and SMQ
- PT level for SAE
- PT level for AE $\geq 2\%$ or incidence rate per 100 subject years ≥ 5.0 in any treatment group
- Other selected AEs of special interest on lower levels (e.g. PT or SMQ level 2), if appropriate

The crude incidence of treatment emergent adverse events will be presented for the treatment period up to Week 16 LPLV for W16 primary analysis, and treatment period including all data for final analysis. The crude incidence of treatment emergent adverse events will be summarized by primary System Organ Class (SOC) and Preferred Term (PT). Confidence intervals for the crude rate will be derived using the score method including continuity correction (Newcombe 1998) as described in [Section 5.4.5](#). In addition, exposure time-adjusted incidence rates will be provided for the treatment period including all data (see [Section 5.4.6](#)).

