Crude rate of important identified and potential risks from Case Retrieval Sheet will be provided for all (non-serious and serious) cases and for all serious cases. Exposure-time adjusted rates will be provided for treatment period including all data for all (non-serious and serious) cases and for all serious cases. In addition, listings will be provided for the related AE risks.

Risk measures and confidence intervals will be derived according to [Section 5](#).

The version of the Case Retrieval Sheet used for the analyses will be described in a footnote. This includes MedDRA version and Novartis MedDRA Query (NMQ) dictionary date.

A separate table of injection site reaction related AEs caused by the 2 mL AI and the 1 mL PFS respectively will be provided. Additional analyses on the severity, outcome, etc. of the AEs caused by AI and PFS respectively may be performed to support health authority interactions as necessary.

Important note: For the evaluation of risks primary and secondary system organ classes of the MedDRA dictionary will be considered.

For the legal requirements of ClinicalTrials.gov and EudraCT, two required tables on adverse events which are not serious adverse events (PT) with an incidence greater than >2% and on SAEs suspected to be related to study treatment will be provided by system organ class and preferred term on the safety set population.

If for a same patient, several consecutive AEs (irrespective of study treatment causality, seriousness and severity) occurred with the same SOC and PT:

- a single occurrence will be counted if there is ≤ 1 day gap between the end date of the preceding AE and the start date of the consecutive AE

- more than one occurrence will be counted if there is > 1 day gap between the end date of the preceding AE and the start date of the consecutive AE

For occurrence, the presence of at least one SAE / SAE suspected to be related to study treatment / non SAE has to be checked in a block e.g., among AE's in a ≤ 1 day gap block, if at least one SAE is occurring, then one occurrence is calculated for that SAE.

The number of deaths resulting from SAEs suspected to be related to study treatment and SAEs irrespective of study treatment relationship will be provided by SOC and PT.

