2.8.4.2 Vital signs

Analysis in vital sign measurement using descriptive summary statistics for the change from baseline for each post-baseline visit will be performed by vital sign and treatment group. Change from baseline will only be summarized for subjects with both baseline and post-baseline values and will be calculated as:

$$\text{change from baseline} = \text{post-baseline value} - \text{baseline value}$$

Only “on-treatment” vital signs will be summarized (i.e. assessments within last dose plus 84 days). All vital signs will be listed with “on-treatment” flag displayed.

The number and percentage of subjects with newly occurring notable vital signs abnormalities will be presented. Criteria for notable vital sign abnormalities are provided in [Table 2-11](#) below. A listing of subjects with newly occurring notably abnormal vital signs will be provided.

Table 2-11 Criteria for notable vital sign abnormalities

Vital sign (unit)	Notable abnormalities
Systolic blood pressure (mmHg)	$\geq 140 \text{ mmHg}$ or $< 90 \text{ mmHg}$
Diastolic blood pressure (mmHg)	$>90 \text{ mmHg}$ or $<60 \text{ mmHg}$
Pulse (bpm)	$> 100 \text{ bpm}$ or $<60 \text{ bpm}$

[REDACTED]

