5.4.5.2 Relative risk and 100*(1- α)% confidence interval

For an investigational drug group with n_1 subjects at risk, independent from the control group (e.g., placebo or comparator) with n_0 subjects at risk, of whom x_1 and x_0 experience a certain event with probability π_1 and π_0 respectively, the relative risk is estimated as p_1/p_0 with $p_1=x_1/n_1$ and $p_0=x_0/n_0$.

An asymptotic $100*(1-\alpha)\%$ confidence interval on the relative risk will be based on the back-transformed large sample confidence limits on the log-transformed relative risk estimate which are obtained by application of the delta-method and Slutsky's theorem (Lachin 2000). The SAS procedure PROC FREQ with option RELRISK in the TABLES statement will be used to provide the asymptotic $100*(1-\alpha)\%$ confidence interval on the relative risk. The estimate is not computed if either x_1 or x_0 equals 0. In this case, or if the crude incidences are low in both groups, the relative risk will be approximated by the odds ratio for which an exact confidence interval will be obtained as specified in [Section 5.4.6.3](#). If the relative risk is not well approximated by the odds ratio but asymptotic normality is questionable, STATAACT will be used.

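### Entire-period safety tables set crude percentages for secukinumab followed to Week 52 beside a placebo column mostly cut at Week 12, and several categories have no stated exposure-adjusted rate

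*SAP*

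**What the plan says.** The safety objective in Protocol Table 2-1 is comparative: safety and tolerability "as assessed by vital signs, clinical laboratory variables, and adverse events monitoring, compared to placebo".

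SAP 1.1 defines the entire treatment period as "Randomization to Week 52, last dose at Week 48". SAP 2.8 lists the columns for that period: the two randomized secukinumab arms, three pooled secukinumab columns, and Placebo, where "all subjects who are re-assigned will only be considered until the re-assignment point (Week 12 treatment injection"). Under Protocol 6.1.3 only placebo subjects who are PASI 90 responders at Week 12 stay on placebo.

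SAP 2.8.1 asks for numbers and percentages of subjects with events by group, over all data at the final analysis. For the earlier cut: "The crude incidence of treatment emergent adverse events will be presented for the treatment period up to Week 16 LPLV for W16 primary analysis". SAP 2.8.4.2 does the same for vital signs: "The number and percentage of subjects with newly occurring notable vital signs abnormalities will be presented".

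The plan also contains two safeguards. SAP 2.8 and Protocol 12.6.2 provide separate tables for Treatment Period 1. Protocol 12.6.2 adds: "Exposure adjusted analyses in terms of incidence rate will be provided combining all the study periods". SAP 2.8.1 implements this for AEs and SAEs by system organ class, SAEs and the more frequent AEs by preferred term, SMQs and important risks. SAP 2.8.3 adds neutropenia of grade 2 or higher.

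**The concern.** A crude percentage counts subjects with at least one event and ignores how long each was observed. If one column is observed for 52 weeks and the other mostly for 12, the longer column shows more subjects with events even when the drug does nothing. Because the objective is a comparison with placebo, readers will compare these adjacent columns.

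Where an exposure-adjusted rate accompanies the percentage, the reader can correct for this. The text of SAP 2.8.1 to 2.8.4.2 specifies no such rate for AEs by severity, treatment-related AEs, liver events, CTCAE worsening other than neutropenia, or notable vital signs. Nor does any sentence confine crude comparisons with placebo to Treatment Period 1. What is at stake is an apparent excess of harm on secukinumab in those summaries that comes from length of follow-up. The efficacy conclusions are not affected.

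**Working it through.** **The plan's own figures.** The documents state no AE rate, mean follow-up or crude ratio, so there is no figure on this point to reproduce. The 8% placebo PASI 90 rate comes from the sample-size sections (Protocol 12.8.2, SAP 3.1.1). With 40 per group and a one-sided 2.5% Fisher's exact test, power for 46% versus 8% is 97.3%, consistent with the stated figure of above 90%.

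**Inputs.** About 120 subjects randomized 2:2:1:1 give 40 AI, 40 PFS and 40 placebo (20 + 20). With 8% PASI 90 responders, 0.92 × 40 = 36.8, about 37 placebo subjects, leave the Placebo column at Week 12. Assumed: the same constant hazard in all groups, no dropout, and a range for 12-week incidence *c*.

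**Mean follow-up.**
- Placebo: 0.92 × 12 + 0.08 × 52 = 15.2 weeks.
- Randomized secukinumab: 52 weeks; 52 / 15.2 = 3.42.
- Any secukinumab, with switched subjects contributing 40 weeks: (80 × 52 + 36.8 × 40) / 116.8 = 48.2 weeks; 48.2 / 15.2 = 3.17.

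**Crude percentages over the entire period.** Secukinumab: S = 1 − (1 − c)^(52/12). Placebo: P = 0.92c + 0.08S.

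| 12-week incidence c | Secukinumab S | Placebo P | Ratio S/P |
|---|---|---|---|
| 1% | 4.3% | 1.3% | 3.38 |
| 5% | 19.9% | 6.2% | 3.22 |
| 10% | 36.7% | 12.1% | 3.02 |
| 20% | 62.0% | 23.4% | 2.65 |
| 30% | 78.7% | 33.9% | 2.32 |
| 50% | 95.0% | 53.6% | 1.77 |

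The ratio falls for common events because crude incidence saturates. It rises with fewer placebo responders: at c = 10% it is 3.39 with 3% responders and 3.67 with none.

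**Week 16 cut.** Replacing 52 by 16 in both formulas gives 1.29 at c = 5%, 1.28 at 10%, 1.26 at 20% and 1.19 at 50%. This assumes each subject is cut at 16 weeks. If the reference to Week 16 LPLV in SAP 2.8 admits later data from early enrollees, the ratio would be larger.

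**Abnormalities found at visits.** SAP Table 2-3 has 6 post-baseline windows to Week 12 (Weeks 1, 2, 3, 4, 8, 12) and 10 to Week 52 (adding 16, 28, 40, 52). With an equal chance of detection per window, the expected ratio is at most 10 / (0.92 × 6 + 0.08 × 10) = 10 / 6.32 = 1.58.

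**After adjustment.** With equal constant hazards, the exposure-adjusted rate of SAP 5.4.6.1 gives an expected ratio of about 1.0. So do Treatment Period 1 crude percentages, because every group has 12 weeks. For visit-detected abnormalities, adjusting for time overcorrects. Windows per week are 10/52 = 0.192 on secukinumab and 6.32/15.2 = 0.416 on placebo, so a rare abnormality with equal chance per window would show a rate ratio near 0.192 / 0.416 = 0.46. Entire-period placebo rates therefore remain descriptive even when adjusted.

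**The case against.** The strongest reply is that the plan already handles most of this. Treatment Period 1 tables give the equal-window comparison, exposure-adjusted rates cover the main AE categories, and SAP 2.4.1 summarizes exposure by group. Stopping re-assigned subjects at the Week 12 injection is also correct attribution, since later events occur on secukinumab. All of that stands.

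It can also be said that SAP 2.8.1 opens by promising both measures for AEs and other binary safety variables. But it does so as described below and in Table 2-8, and the text below gives no adjusted rate for the categories named above. The cells of Table 2-8 are broken in the text available, so blanks there are not used as evidence either way. If the original table marks adjusted rates for those categories, that part of the gap closes.

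Three stronger readings are tempting and not supported:

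- A reader might infer that the plan will report relative risks against placebo over the entire period and so produce formally significant false harm. SAP 2.8.1 does say "Risk measures and confidence intervals will be derived according to" Section 5, and SAP 5.4.5.2 defines a relative risk for a drug group "independent from the control group (e.g., placebo or comparator"). These are general formulas. No passage orders an entire-period relative risk, odds ratio or risk difference, Section 5 also holds the exposure-adjusted methods, and SAP 2.1 keeps confidence intervals out of decision making. The period is left open; the analysis is not shown to be planned.
- A reader might take three-fold as general. It applies only to uncommon AEs; it does not apply to common ones, to visit-detected abnormalities, or to the Week 16 analysis.
- A reader might conclude that the entire-period Placebo column should go. Protocol Section 12 lists placebo among the entire-study groups, and the column holds the later events of placebo PASI 90 responders.

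**Conclusion.** The concern holds in a limited form. In entire-period tables, crude percentages stand side by side over mean windows of about 15 and 52 weeks, and the resulting ratio under no drug effect is material at the final analysis for uncommon AEs. It is modest for visit-detected abnormalities and small at Week 16. The sizes rest on an assumed constant and equal hazard, no dropout, the plan's 8% placebo PASI 90 rate and assumed 12-week incidences.

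The uncorrected part is confined to summaries for which the text specifies only crude percentages, together with the missing statement that crude comparison with placebo belongs to Treatment Period 1.

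**What to change.** In SAP 2.8, 2.8.1 and Table 2-8:

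1. State that crude incidences, and any relative risk, odds ratio or risk difference from SAP 5.4.5 if produced, are compared with placebo in Treatment Period 1 only.
2. Keep the entire-period Placebo column, but show subject-years for every column.
3. Extend the exposure-adjusted incidence rate of SAP 5.4.6.1 to every category that keeps that column, including AEs by severity, treatment-related AEs, liver events, CTCAE worsening and notable vital signs.
4. Label entire-period placebo figures descriptive, because after Week 12 visits are sparser and only placebo PASI 90 responders remain.

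The cost is SAP wording and a few extra table rows. No new data are needed, and the protocol's list of treatment groups is unchanged.
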